3.3.3. Re-randomized Population Analyses

For the mNIS+7/NIS individual components, total scores, and related endpoints, and 10-MWT, baseline will be defined as the last nonmissing derived value before the first dose in the RTE Period. In most cases, this will correspond to the Month 18 derived values.

For all other efficacy and all safety parameters, unless noted otherwise, baseline will be defined as the last nonmissing measurement before the first dose in the RTE Period.

Baseline ADA status will be defined as the last nonmissing anti-TTRSC02 ADA assay measurement before the first dose in the RTE Period. In most cases, this will correspond to the RTE Day 1 measurement.

For PD parameters (TTR, Vitamin A), baseline will be defined the same as for the 18-Month Treatment Period (Section 3.3.1).

3.4. Randomization Stratification Factors

Stratification factors for randomization into the 18-Month Treatment Period include TTR genotype (V30M vs. non-V30M) and baseline NIS score (< 50 vs. ≥ 50).

Stratification factors are recorded in both the Interactive Response System (IRS) and the clinical database. In statistical analyses that use randomization stratification factors as covariates, the stratum assignment will reflect the values as recorded in the clinical database. In the presence of stratification errors, the stratification used in analysis may not match that in the IRS.

In addition to the initial randomization, [REDACTED]

[REDACTED] For patients initially randomized to vutrisiran, stratification factors for this 2nd randomization include TTR genotype (V30M vs. non-V30M) and the most recent FAP stage (0/1 vs 2/3) before the 2nd randomization. For patients initially randomized to patisiran, there is no stratification for this 2nd randomization.

3.5. Efficacy Censoring Rules

The censoring rules are applicable to analyses described in Section 4 for the 18-Month Treatment Period.

3.5.1. Initiation of Local Standard Treatment for hATTR Amyloidosis

In the APOLLO study, there were placebo-treated patients who discontinued study drug, but remained on study and received local standard treatment. For the primary analysis of mNIS+7 and Norfolk QoL-DN, assessments were censored (excluded from analysis) after initiation of any of the following:

- Orthotopic liver transplant
- Use of TTR stabilizing agents (eg, tafamidis, diflunisal) for >14 days

For consistency of data handling, the placebo group from the APOLLO study will follow the same censoring rule as the APOLLO study.

For this study, APOLLO censoring rules will be applied. Additionally, assessments will be censored after initiation of any of the following recently approved treatments:

- Any use of TTR-targeting anti-sense oligonucleotides (eg, inotersen)
- Any use of patisiran (applicable for the vutrisiran treatment group only)

This data will be included and flagged in efficacy listings. These assessments from either study will be included in sensitivity analyses as specified.

For TTR percent reduction, TTR assessments collected after initiation of local standard treatment for hATTR amyloidosis will be excluded from the analysis. For all other efficacy endpoints, data

from either study collected after initiation of local standard treatment for hATTR amyloidosis will be included in analyses.

A separate listing will be provided for patients who initiate local standard treatment for hATTR amyloidosis while on study.

3.5.2. Onset of Serious COVID-19 Adverse Events

Patients who experience a serious COVID-19 AE may have worsening in general health and wellbeing unassociated with the natural course of hATTR amyloidosis or with study drug. Assessments will be censored on or after the onset of a serious COVID-19 AE for all analyses of mNIS+7, Norfolk QoL-DN, 10-MWT, mBMI, and R-ODS, and any associated component/domain scores. This will reflect a hypothetical estimand of interest where the COVID-19 pandemic did not occur, as was the case for placebo group from the APOLLO study.

3.6. Missing Data with Efficacy Endpoints

All efficacy data collected during study, regardless of whether before or after treatment discontinuation, will be included for analyses, with the exception of mNIS+7 and Norfolk QoL-DN collected post local standard treatment for hATTR amyloidosis (discussed in Section 3.5), and mNIS+7, Norfolk QoL-DN, 10-MWT, mBMI, and R-ODS on or after the onset of a serious COVID-19 AE (Section 3.5.2).

3.6.1. Missing Subcomponents within Primary and Secondary Efficacy Endpoints

For each patient, missing subcomponents within the primary mNIS+7 endpoint and secondary efficacy endpoints will be imputed whenever possible according to the algorithms specified in Section 9.1. When this “partial imputation” is successful (ie, complete mNIS+7 values are produced), these values will be used in all statistical analyses. When partial imputation is unsuccessful, the efficacy endpoint will be treated as completely missing.

3.6.2. Summary of Missing Data

For each of the primary and secondary efficacy endpoints, the number and percentage of missing data (completely missing), including due to COVID-19, at each visit (Baseline, Month 9, and Month 18) will be summarized by study group.

Summary of missing data for the primary and secondary efficacy endpoints during the RTE period may be provided, including due to the COVID-19.

3.7. Visit Windows

It is expected that all visits should occur according to the protocol schedule. All data will be tabulated and analyzed per the evaluation visit as recorded on the electronic case report form (eCRF) even if the assessment is outside of the visit window.

For efficacy assessments, if the scheduled visit (eg, Month 9) is not performed, the unscheduled and/or discontinuation visits performed within a ± 3 -month window will be grouped with the scheduled visit. In situations in which a Month 9 or Month 18 efficacy visit is unable to be completed due to the Coronavirus disease 2019 (COVID-19) pandemic limiting the patient’s ability or willingness to access the study center or their ability to have received their scheduled

doses of study drug, Month 9 and Month 18 efficacy assessments may be completed within 6 months after the intended time point (ie, up to Study Month 15 or Month 24, respectively). For patients impacted by the COVID-19 pandemic, efficacy visits delayed up to 6 months after the end of the protocol-defined efficacy visit window will be included in the analysis. The derived visits will be used for all analyses. [REDACTED]

Unless otherwise specified above, data collected at unscheduled visits will be included in by-patient data listings and figures, but no assignment to a study visit will be made for the purpose of by-visit summary tabulations. However, unscheduled visits may be used in the calculation of baseline values (as discussed in Section 3.3) and for inclusion in any categorical shift summaries (e.g., shift from baseline to “worst” postbaseline value).

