During the Treatment Extension Period, starting at Week 84/Month 19, all patients on the patisiran group will switch to treatment with vutrisiran (first dose) and remain on vutrisiran q3M treatment for the remainder of the study. During the Treatment Extension Period, patients will undergo safety assessments quarterly and efficacy assessments every 9 months at Month 27 and at Month 36.

During the Follow-up Period, all patients on vutrisiran will undergo safety assessments quarterly until serum TTR levels return to \geq 80% of baseline (for up to 1 year after the last dose of study drug), or until the patient starts a TTR lowering regimen as a part of clinical care, whichever comes first; all patients will be followed for a minimum of 3 months. Female patients of child-bearing potential will be followed until serum TTR levels return to \geq 80% of baseline. Patients

who discontinue treatment early while on patisiran will undergo a follow-up visit 30 days after the last dose of study drug.

The placebo group of the APOLLO (ALN-TTR02-004) study will be used as an external control for the primary, most secondary, and most exploratory efficacy analyses. Primary and secondary efficacy evaluations will include mNIS+7, Norfolk QoL-DN questionnaire, 10-MWT, mBMI, R-ODS questionnaire, and percent TTR reduction. Study personnel performing the mNIS+7 component assessments will not reference the results of any previous assessments.

Figure 1: Study Design

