3.2. General Methods

All data listings that contain an evaluation date will contain a study day relative to the day of the first dose of study drug, which is designated as Day 1. On-treatment study days will be calculated as evaluation date – first dose date +1 and pretreatment days will be calculated as evaluation date – first dose date. There is no Day 0.

Categorical descriptives will include the count and percentage of patients (or events, if applicable) within each category (with a category for missing data) of the parameter. Continuous descriptives will include the number of patients, mean, median, standard deviation (SD), standard error (SE), minimum, and maximum values.

Laboratory data (including vitamin A) collected and recorded as below the limit of detection will be set equal to the lower limit of detection for the calculation of summary statistics.

For assessments that are repeated multiple times for the study visit, the average will be calculated unless otherwise noted.

All summaries will be presented by treatment group. Unless otherwise specified, treatment groups in the Treatment Period will be presented using the following labels:

- Placebo (APOLLO)
 - Presented primarily for efficacy (except TTR) analyses and most safety and baseline summaries
- Vutrisiran (HELIOS-A)
- Patisiran (HELIOS-A)
- Total (HELIOS-A)
 - Presented primarily for patient disposition, protocol deviations, and baseline summaries

In addition, for TTR sensitivity analyses, the following treatment groups will be presented:

- Patisiran (HELIOS-A + APOLLO)
- Patisiran (APOLLO)

For analyses on the All Vutrisiran-Treated Population, the following treatment arms will be presented:

- Vutrisiran/Vutrisiran
- Patisiran/Vutrisiran
- Total

These 3 treatment arms represent the respective Vutrisiran (HELIOS-A), Patisiran (HELIOS-A), and Total (HELIOS-A) treatment groups, reflecting the transition from the initial randomized treatment (either vutrisiran or patisiran) during the Treatment Period to vutrisiran in the subsequent Legacy Treatment Extension or RTE periods. The experience while receiving vutrisiran will be summarized.

For analyses on the Re-randomized Population, the following treatment groups will be presented:

- Vutrisiran 25 mg q3M
- [REDACTED]
- Total

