4.7.1. Study Drug Exposure

Last exposure date during the 18-month Treatment Period is defined as the earliest of the following dates:

- Last dose date + treatment-specific window (83 days for vutrisiran; 20 days for patisiran)
- Analysis cutoff date
- End of study date
- Week 84 dose date (start of Legacy Treatment Extension Period)
- RTE Day 1 dose date (start of RTE Period)

Duration of drug exposure will be defined as last exposure date – first dose date + 1. Duration of drug exposure, the total number of doses received, and total amount of study drug received will be summarized by descriptive statistics. Summaries of the numbers and percentages of patients

with no missing dose, and the number of missing doses per patient will also be provided. The total volume infused or injected will be summarized as well.

Study drug exposure data collected in the CRFs of study drug administration will also be summarized for each dose or infusion. The numbers and percentages of patients with complete, partial, and missing dose administrations will be summarized. Complete and partial administration is defined as follows:

- Patisiran:
 - Complete: $\geq 80\%$ (≥ 160 mL) of the planned infusion volume (200 mL)
 - Partial: $> 0\%$ to $< 80\%$ (> 0 to < 160 mL) of the planned infusion volume (200 mL)
- Vutrisiran:
 - Complete: 100% administered
 - Partial: $> 0\%$ to $< 100\%$ administered

For the patisiran group, the number of patients who experienced interruptions of infusions for any reason will be tabulated, as well as the number of patients with infusion interruptions due to an infusion-related reaction (IRR).

For the vutrisiran group, the above drug exposure summaries applicable to vutrisiran will also be provided by vial vs prefilled syringe dose presentations. Vutrisiran doses with missing dose presentation information before the date of first prefilled syringe administration to any patient will be treated as vial dose presentations.

Duration of exposure to vial and prefilled syringe dose presentations of vutrisiran will also be summarized.

Dosing information for each patient will be presented in a data listing.

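### Month 18 efficacy values may be taken after the Week 84 or RTE Day 1 dose, and no visible rule stops a value taken after a change of drug or regimen from counting for the original arm

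*SAP*

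**What the plan says.** All references are to SAP Amendment 3 unless stated otherwise.

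- **Window.** Section 3.7 analyses data under the visit named on the eCRF, even when the date is out of window. If the scheduled visit was not done, unscheduled visits and "discontinuation visits performed within a ± 3 -month window will be grouped with the scheduled visit". For COVID-19 it allows assessment within 6 "months after the intended time point (ie, up to Study Month 15 or Month 24, respectively". The next sentence sets the limit differently: "efficacy visits delayed up to 6 months after the end of the protocol-defined efficacy visit window will be included in the analysis".
- **End of the Treatment Period.** For exposure, Section 4.7.1 takes the earliest of several dates. Two of them are "Week 84 dose date (start of Legacy Treatment Extension Period" and "RTE Day 1 dose date (start of RTE Period".
- **What changes then.** Section 3.2 describes the extension arms as "reflecting the transition from the initial randomized treatment (either vutrisiran or patisiran) during the Treatment Period to vutrisiran". Amendment 2, Section 1.1, gives the timing for the former extension: "starting at Week 84/Month 19, all patients on the patisiran group will switch to treatment with vutrisiran (first dose". Section 3.4 provides for a second randomisation. Section 3.2 lists a second, redacted group beside 25 mg q3M, and Section 6.2 gives two follow-up windows (83/84 and 167/168 days) according to the last vutrisiran dose.
- **Exclusions.** Sections 3.5 and 3.6 remove data after local standard treatment (mNIS+7, Norfolk QoL-DN and TTR) and data from the onset of a serious COVID-19 AE. Patisiran use leads to censoring in the vutrisiran arm only. The start of an extension period is not on the list.
- **RTE baseline.** Under Section 3.3.3, "baseline will be defined as the last nonmissing derived value before the first dose in the RTE Period". The SAP expects this to be the Month 18 value in most cases, so not in all.

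**The concern.** The SAP treats the first extension dose as the end of the randomised period when it counts exposure, but not when it assigns efficacy values to Month 18. An assessment made after the patient changed drug or regimen can therefore be analysed as the Month 18 result of the original arm.

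Two things are at stake. In the patisiran arm, a value obtained on vutrisiran would appear in the patisiran column. In the vutrisiran arm, a patient re-randomised to the second RTE regimen before a delayed Month 18 visit could contribute that regimen's outcome to Month 18 mNIS+7. Section 1.3.2 makes that the primary endpoint for the EU and other regions, and Section 4 is meant to describe the initial 18-month Treatment Period.

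**Working it through.** **Inputs.** Month 18 plus 3 months, and Month 18 plus 6 months (Section 3.7); Legacy extension at the Week 84 dose (Section 4.7.1); 30.4375 days per month (exposure formula in Amendment 1, Section 4.7.1); about 160 patients at 3:1 and an assumed 15-point mNIS+7 difference at Month 9 (Section 1.4).

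**The plan's own limits.** 9 + 6 = 15 and 18 + 6 = 24, which reproduces the stated Months 15 and 24. The substitute-visit limit is 18 + 3 = Month 21. Counted from the end of the visit window, the COVID-19 limit is Month 24 plus the window's late tolerance. The SAP does not give that tolerance, so the two sentences in Section 3.7 set different limits.

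**Week 84 in months.** 84 × 7 = 588 days; 588 / 30.4375 = 19.32 months. This agrees with the Week 84/Month 19 pairing in Amendment 2.

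**Overlap with the Legacy extension.**
- To Month 21: 21 − 19.32 = 1.68 months. In weeks, 21 × 30.4375 / 7 = 91.3, and 91.3 − 84 = 7.3.
- To Month 24: 24 − 19.32 = 4.68 months. In weeks, 24 × 30.4375 / 7 = 104.4, and 104.4 − 84 = 20.4.
- On a 12-week grid, one extension dose (Week 84) falls inside the Month 21 limit and two (Weeks 84 and 96) inside the Month 24 limit.

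**Overlap with the RTE.** It cannot be computed, because the calendar timing of RTE Day 1 is not visible.

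**Which analyses the overlap can reach.**
- *Patisiran arm:* Section 4.4 puts only vutrisiran and APOLLO placebo in the non-TTR models, with simple descriptives for patisiran. The arm has about 160 / 4 = 40 patients, so each affected patient is 1/40 = 2.5% of that column.
- *Vutrisiran arm, Legacy extension:* the drug stays the same.
- *Vutrisiran arm, RTE:* a patient assigned the second regimen before a delayed Month 18 visit enters the Month 18 model under the original arm.
- *TTR noninferiority:* the qualifying troughs run from Week 24 to Week 72 (Section 2), before Week 84.

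**Size per patient, as an illustration.** The vutrisiran arm has about 160 × 3/4 = 120 patients. If one re-randomised patient's value differed by d points from what the original regimen would have given, the unadjusted arm mean moves by d/120. Taking d as large as the whole assumed Month 9 difference gives 15/120 = 0.125 points per affected patient. The Month 9 figure is borrowed, because Section 1.4 gives none for Month 18.

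**Does a planned analysis isolate the problem?** The Month 18 Efficacy PP population requires a visit within 3 calendar months of the window and all doses through Week 72 with at most 28 days' delay. It drops the longest delays, but it still reaches past Week 84 and has no criterion on extension doses.

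**The case against.** The strongest reply is that the overlap may be empty in practice. The unseen protocol may require the Month 18 assessments before any extension dose. A redaction follows the window rules in Section 3.7, and the RTE design is also redacted. The ±3-month route is narrow: a patient seen at a treatment-discontinuation visit is not moving on to a new regimen, which leaves an unscheduled efficacy visit after extension dosing with Month 18 missed. The COVID-19 route needs a pandemic cause and consultation with the Medical Monitor (Section 1.1). The SAP also chose to keep as much efficacy data as it could.

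Most of this limits the size and stands. It does not supply the rule. The amendment log describes the Section 3.7 addition as a window for the RTE visit, so a cap on Month 18 there is unlikely, though this cannot be confirmed. Because Section 3.7 analyses data whatever their date, the SAP needs a rule for exceptions even if the protocol fixes the order.

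A reader might also infer more than the document supports:
- *That the patisiran-to-vutrisiran switch contaminates the Month 18 superiority tests.* It does not, because patisiran is outside those models.
- *That the 1.7 and 4.7 months measure the exposure of the EU primary endpoint.* They count from Week 84, which starts the Legacy extension only, where vutrisiran patients stay on vutrisiran.
- *That every affected patient's RTE baseline falls back to Month 9.* Section 3.3.3 refuses only values after the first RTE dose. A value taken after Week 84 but before RTE Day 1 remains eligible, and a fallback to Month 9 is inference.

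**Conclusion.** The point holds in a limited form. As written, Section 3.7 can assign to Month 18 an efficacy value taken after a change of drug or regimen, and no visible text in Sections 3.5 to 3.7 prevents it. Section 4.7.1 already makes the corresponding cut for exposure.

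For patisiran, the consequence is a mislabelled value in a descriptive column. For the Month 18 mNIS+7 comparison, the only route is a vutrisiran patient re-randomised to the second regimen before a delayed visit. How many such patients there are is unknown. The number is probably small, since the SAP expects Month 18 values to precede RTE dosing in most cases. No effect on a tested result is shown.

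The conclusion assumes that the redacted text holds no cap and that RTE Day 1 can precede a delayed Month 18 visit for some patients.

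**What to change.** State in Sections 3.5 and 3.7 that an efficacy assessment on or after the first extension dose that changed the patient's drug or regimen is not assigned to Month 18. Treat it as missing there, flag it in the listings, and run a sensitivity analysis that includes it. Patients who continue the same vutrisiran regimen keep their value. Apply the same rule to the Month 18 Efficacy PP population.

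Also reconcile the two six-month limits in Section 3.7, so that the count starts either from the intended time point or from the end of the visit window, but not both.

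The cost is a sentence or two in the SAP, a date check in programming and one extra model run. The downside is a few more missing Month 18 values. In the vutrisiran arm these are handled by the planned MMRM (Section 4.4.1.2) and the Month 18 pattern-mixture model (Section 4.4.2.3). The sensitivity analysis respects the SAP's aim of keeping observed data.

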3.8. Interim Analyses

No interim analysis is planned for this study.

3.9. Planned Analyses

As this study will be ongoing at the time of the primary analysis at Month 9 and the additional analysis at Month 18, the study database will undergo an interim database lock at the Month 9 and Month 18 data cutoff dates (ie, data in EDC will be cleaned, frozen and electronically signed by investigators; external laboratory data will be cleaned and will undergo quality assurance). Additional details regarding the interim database locks will be documented in the study Data Management Plan.

The Month 9 and Month 18 analyses and associated clinical study reports (CSRs) will include all data on or before the respective data cutoff date. For assessments with start and end dates (eg, AEs, medications, medical history), data records with start dates after the specified data cutoff date will be excluded.

[REDACTED]

After the study is completed (ie, all patients discontinue or complete the RTE Period and/or required follow-up visits), the database will undergo a final database lock, and the data will be summarized in a final CSR.

4. ANALYSIS OF THE 18-MONTH TREATMENT PERIOD

The primary objective of this study is to evaluate the efficacy and safety of vutrisiran during the initial 18-month Treatment Period; analyses described in this section focus on this objective.

4.1. Patient Disposition

Patient disposition will be tabulated for all randomized patients and will include categorical descriptives for the following parameters:

- Patients in each analysis population
- Patients randomized

- Patients treated
- Patients who complete or discontinue treatment
 - Primary reasons for treatment discontinuation and discontinuation due to COVID-19
- Patients who discontinue treatment before Month 18
 - Primary reasons for treatment discontinuation and discontinuation due to COVID-19
- Patients who discontinue treatment after Month 18
 - Primary reasons for treatment discontinuation and discontinuation due to COVID-19
- Patients who complete study participation
- Patients who stop study participation
 - Primary reasons for stopping study participation and stopping study participation due to COVID-19

Patient disposition by country and site will be summarized by randomized treatment group and overall. The number and percent of patients in each randomization stratification factor recorded in IRS, and a comparison of the number and percent of patients in each randomization stratification factor in IRS versus the clinical database will be summarized by randomized treatment group and in total.

Data listings of treatment/study completion information including the reason for treatment discontinuation and/or stopping participation in the study will be presented.

